Vitamin D Supplementation on Physical and Cognitive Function-Pilot Study

PI: [name]

NCT01229878

2/13/2012

PART II
RESEARCH PROPOSAL

A) SPECIFIC AIMS.

Current practice guidelines from the National Kidney Foundation (NKF) do not require monitoring for or correction of 25-OH vitamin D deficiency. Instead, the guidelines for vitamin D therapy in hemodialysis (HD) patients recommend using active (1,25 OH) vitamin D to suppress serum parathyroid hormone (PTH) levels to a recommended range of 150-300 pg/ml. The current NKF guidelines for vitamin D therapy in HD patients focus on narrowly maintaining biomarkers of skeletal health and fail to address the important functions of vitamin D on extra-skeletal tissue. Despite the current vitamin D regimen recommended by the NKF, HD patients have a very high prevalence of 25-OH vitamin D deficiency. At the same time, HD patients experience muscle weakness, muscle fatigue, and cognitive impairment all of which have been associated with 25-OH vitamin D deficiency in the general population. Our broad long-term objective is to improve muscular strength, postural balance, muscular performance, and cognition by supplementing HD patients with vitamin D deficiency (<20 ng/ml). Our goals in this pilot study are to 1) assess the feasibility of recruiting and retaining HD patients in this study, 2) evaluate the proposed regimen for safely increasing 25-OH vitamin D levels with oral supplementation 3) develop the knowledge and experience with critical outcome measures for a future pivotal trial to assess the benefits of vitamin D supplementation on function and cognition in the HD population. We will accomplish this through a feasibility study with the PRIMARY objective to determine the effect of vitamin D supplementation on neuromuscular and cognitive functioning in HD patients by performing a feasibility study. Our hypothesis is that muscle strength, muscle performance, postural balance, and cognitive function will improve after vitamin D has been supplemented into the normal range (≥ 30 ng/ml).

In patients with chronic kidney disease who are on HD, we propose to perform a 6 month randomized, double blind, placebo-controlled trial to determine the feasibility of the following specific aims (SA):

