The current standard of care involves the administration of active 1,25 OH vitamin D intravenously during dialysis. The dose is determined by the patient's private nephrologist based on monthly laboratory reports. Because 25-OH vitamin D supplementation is not currently recommended in HD patients, only a limited number of studies have examined the efficacy and safety of cholecalciferol and ergocalciferol vitamin D replacement in this population. Currently two studies have evaluated the safety and efficacy of 25-OH replacement in HD patients over a 6 month duration. In one study, oral 25- OH vitamin D was given daily in doses ranging from 400 units to 1200 units based on severity of vitamin D deficiency (45). All patients had 25-OH vitamin D levels < 30 ng/mL and 87% achieved levels > 30 ng/mL without evidence of toxicity. In another study in which 52% of patients had 25-OH < 15 ng/ml and 92% had levels < 30 ng/mL; after 6 months of treatment using 50,000 U of ergocalciferol, 94% of patients had 25-OH levels > 30 ng/mL and none were < 15 ng/mL (2). The treatment was well tolerated without evidence of toxicity. The safety of cholecalciferol administration to HD patients was demonstrated after 100,000 units of cholecalciferol were given monthly for 15 months; vitamin D deficiency was corrected in nearly 90% of patients (46). Using more frequent doses of vitamin D, 20,000 units of cholecalciferol were given weekly to HD patients with levels < 15 ng/mL for 9 months and followed up with maintenance dosing at 20,000 per month for 15 months; vitamin D was well tolerated and without adverse effects, however only 57% of patients achieved levels > 30 ng/mL which is considered optimal (47). Given the safety of these studies, we propose administering 50,000 units of cholecalciferol every week with level monitored monthly to insure response to treatment and to adjust dose if levels raise > 60 ng/mL. Patients in both arms of the study will receive the current standard of

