We propose to perform a prospective, randomized, double-blind placebo controlled trial. Patients will be included if they are: 1) receiving outpatient hemodialysis at the James J. Peters VAMC, 2) receiving IV vitamin D therapy according to National Kidney Foundation guidelines, 3) between the ages of 45-89 years, 4) a veteran outpatient or stable community living center patient, and 5) able to ambulate independently or with an assistive device for at least 20 feet. Exclusion criteria include: 1) 25-OH vitamin D level \geq 25 ng/ml, 2) hypercalcemia, 3) active malignancy within 6 months, 4) receiving intravenous antibiotics for infection, 5) history of dementia, 6) hemoglobin $<$ 8.5g, 7) history of conditions that interfere with postural instability (e.g. cerebellar disease, vestibular disease or any others that may present), and 8) poor compliance with dialysis treatments (history of skipping \geq 2 treatments per month for $>$ 2 months). A 25-OH vitamin D level of $<$ 25 ng/ml level was chosen based on previous studies that have shown that patients have the greatest improvement in muscle strength when levels below this threshold are increased. Patients will first be identified based on the inclusion criteria, then informed about the study and consented. Those who meet the exclusion criteria will be randomized to treatment or placebo. Enrolled participants will be randomized 2:1 to receive vitamin D (n=20) or placebo (n=10) for 6 months. All participants will be tested twice over two weeks to establish baseline values. Following baseline testing, the treatment group will receive 50,000 IU (standard replacement therapy) of oral cholecalciferol or placebo. The initial dose of cholecalciferol will be 50,000 IU weekly for 6 weeks. Vitamin D levels will then be measured. Participants who still have Vitamin D insufficiency (\leq 35 ng/ml) will remain on 50,000 IU of cholecalciferol for another 6 weeks, at which point Vitamin D levels will be measured again. Participants who reach 25-OH levels $>$ 35 ng/ml will have their dosing regimen lessened to 10,000 IU weekly (maintenance dose) for the remainder of the 6 months. Participants receiving placebo will start taking the placebo maintenance dose after the first 6 weeks. For safety monitoring, 25(OH) vitamin D₃ levels will also be re-measured at monthly intervals and followed by an independent medical monitor. In patients who have serum vitamin D levels \geq 60

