Immune Function Analysis Primary analysis will compare study subjects who had a 25-OH level > 35 ng/ml to study subjects who remained at a level ≤ 35 ng/ml (Vitamin D deficient/insufficient). Potential confounders that will be examined include age, 25-OH Vitamin D level at Baseline, time on HD, sex, and ethnicity. Variables that differ significantly between treatment arms at an alpha of 0.01 and are significantly related to the immune outcomes at an alpha of 0.05 will be included in multivariable analysis. If potential confounders meet the criteria for inclusion, the multivariable analysis will be the primary analysis.

a. Basic Information (Even if described under “Procedures”, list the information requested below where pertinent.)

1. What procedures will be used (i.e. biopsy, surgical operation, interview, experimental diet, infusion, drug administration, etc.) and with what frequency?

All participants will have their serum Vitamin D levels tested twice over two weeks to establish baseline values. Following baseline testing, the treatment group will receive 50,000 IU (standard replacement therapy) of oral cholecalciferol or placebo. The initial dose of cholecalciferol will be 50,000 IU weekly for 6 weeks. Vitamin D levels will then be measured. Participants who still have Vitamin D insufficiency (≤ 35 ng/ml) will remain on 50,000 IU of cholecalciferol for another 6 weeks, at which point Vitamin D levels will be measured again. Participants who reach 25-OH levels > 35 ng/ml will have their dosing regimen lessened to 10,000 IU weekly (maintenance dose) for the remainder of the 6 months. Participants receiving placebo will start taking the placebo maintenance dose after the first 6 weeks. 25(OH) vitamin D₃ levels will also be re-measured at monthly intervals and followed by an independent medical monitor. In patients who have serum vitamin D levels ≥ 60 ng/ml, the frequency of administration will be reduced to once a month. The participants will receive supplementation for a total of 6 months.

The following outcomes will be tested at **Baseline, 3 months and 6 months**:

Physical Functional assessments:

- 1) Neuromuscular functional performance using the 50ft timed walk, TUG test, a timed stair climb, and Chair Raise test, (48)
- 2) Postural stability using a Sway meter (NeuroCom International, Inc., Clackamas, OR) that measures displacement of the body at the level of the waist in 30 second periods (49) and the Functional Reach Test.

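### The immune analysis groups participants by whether 25-OH vitamin D ever passed 35 ng/ml, with no visit named, and its label for 35 or below conflicts with the normal range given elsewhere

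*Combined protocol and SAP*

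**What the plan says.** Section C, Statistical Analysis Plan, Immune Function Analysis: the primary immune analysis will "compare study subjects who had a 25-OH level > 35 ng/ml" with those who "remained at a level ≤ 35 ng/ml (Vitamin D deficient/insufficient". No visit is given for the classifying level, and no rule for repeated readings.

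The dosing text in Research Design and Methods, repeated in Basic Information items 1 and 2, uses the same number: "Participants who still have Vitamin D insufficiency (≤ 35 ng/ml) will remain on 50,000 IU". Once above 35, participants "will have their dosing regimen lessened to 10,000 IU weekly (maintenance dose) for the remainder of the 6 months".

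Two other places use 30. Section A, Specific Aims, states its hypothesis for the situation where "vitamin D has been supplemented into the normal range (≥ 30 ng/ml". In section B, the discussion of dosing in HD patients reports of a cited study that "only 57% of patients achieved levels > 30 ng/mL which is considered optimal".

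Table 1 schedules vitamin D at month 1, week 6 and months 2 to 6, which is seven post-baseline readings. Cytokines are measured at baseline and month 6 only. A 25-OH level of 25 ng/ml or more is an exclusion criterion.

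**The concern.** There are two separate problems in one sentence.

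The first is timing. The two groups are described asymmetrically: one *had* a level above 35, the other *remained* at or below it. Participants must be below 25 at entry, so all should start in the lower range, and the natural reading is that a single crossing moves a participant up for good. Crossing 35 also triggers the step-down in dose, so a later fall is foreseeable. Someone at 36 in week 6 and well below that at month 6 would count as replete when the cytokines are drawn. Because no rule is stated, two analysts could also form different groups from the same data.

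The second is the label. A participant whose level peaks at 32 is in the normal range in the Specific Aims and deficient or insufficient in the immune analysis.

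At stake is whether the achieved-level contrast reflects vitamin D status at the time of the immune measurement, and whether its groups mean what their labels say.

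**Working it through.** The plan gives no figure to reproduce, so the two defects follow from comparing the text. Their size needs assumptions about 25-OH levels on treatment, which the documents do not supply.

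**Inputs from the documents:** 20 treated and 10 placebo; seven post-baseline readings; cut-off 35; normal range from 30.

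**Assumptions, not in the documents:** each treated participant has a personal mean b, normal with mean μ (34 to 45) and SD 8. The seven readings vary independently around b with SD 4. Placebo participants never exceed 35.

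**Any-reading rule.** Let q(b) = Φ((35 − b)/4), the chance that one reading is 35 or less.

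- Month-6 level 35 or less: P_F = E[q(b)] = Φ((35 − μ)/√(8² + 4²)) = Φ((35 − μ)/8.94)
- Never above 35: P_N = E[q(b)⁷]
- Upper group but month-6 level 35 or less: 20 × (P_F − P_N)
- Never above 35 and month-6 level 30 to 35: 20 × E[q(b)⁶ × {Φ((35 − b)/4) − Φ((30 − b)/4)}]

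For μ = 34, P_F = Φ(0.112) = 0.544, or 10.9 of 20. The expectations over b were integrated numerically. Expected numbers of the 20 treated (differences taken before rounding):

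| μ | Month 6 ≤ 35 | Never > 35 | Upper group, month 6 ≤ 35 | Never > 35, month 6 at 30–35 |
|---|---|---|---|---|
| 34 | 10.9 | 6.0 | 4.9 | 1.15 |
| 36 | 9.1 | 4.5 | 4.7 | 0.95 |
| 40 | 5.8 | 2.1 | 3.6 | 0.55 |
| 45 | 2.6 | 0.7 | 2.0 | 0.20 |

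So about 2 to 5 of 20 are in the upper group with a month-6 level of 35 or less. As a share of that group this is 4.9/14.0 = 35% at μ = 34 and 2.0/19.3 = 10% at μ = 45. With mean 30 to 40 and within-person SD 3 to 6, a simulation gave 14% to 33% of treated participants, or 2.9 to 6.5 of 20.

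Nobody with a month-6 level above 35 can be in the lower group under this rule, because that reading itself places them in the upper group.

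**Grouping on the month-6 value instead.** With total SD σ:

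- treated in the band = 20 × {Φ((35 − μ)/σ) − Φ((30 − μ)/σ)}
- lower group = 10 + 20 × Φ((35 − μ)/σ)

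At μ = 36, σ = 8 the band holds 4.47 and the lower group 19.0, a share of 4.47/19.0 = 24%. At μ = 34, σ = 12 it is 3.28/20.7 = 16%. Over μ 34 to 40 and σ 8 to 12 the band holds 2.7 to 4.8 of 20, or 16% to 24% of the lower group. At μ 45 to 50 it falls to 0.5 to 1.9 of 20, or 5% to 14%.

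**Limit of the model.** It holds each personal mean constant. Actual levels would rise during loading and may fall after the step-down, so the counts show order of magnitude only.

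**The case against.** The best defence is that 35 is no slip. It is the trial's operational cut-off for insufficiency, stated in the same terms wherever the dosing schedule is given, and the immune analysis follows it. The level above 30 called optimal is a background remark on a cited study. That stands: the immune paragraph should not be presented as the outlier. But it explains the source of 35 without removing the second definition in the Specific Aims.

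A reader might infer that the any-reading rule sends replete participants into the deficient group. It does the reverse: it keeps participants whose level has fallen in the upper group. Only the label mismatch puts participants who are normal by the Specific Aims in the lower group, and only those at 30 to 35.

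A reader might also infer that 16% to 24% of the lower group is mislabelled and that the contrast shrinks by as much. That share requires grouping on the month-6 value, so it cannot be claimed together with the any-reading rule. The shrinkage further requires the whole immune effect to appear at exactly 30, which nothing in the documents supports.

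Nor does the plan fail to test its own hypothesis on this account. The hypothesis that cites 30 concerns muscle, balance and cognition. The immune hypothesis, H4, gives no threshold.

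Finally, immune function is a secondary outcome in a 30-person pilot, and the same sentence has a larger problem: SA4 promises a comparison by randomized arm. That also stands, and it limits the weight of this point.

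**Conclusion.** The concern holds as a minor point. The classifying reading is undefined, and the literal wording lets any past reading above 35 fix the group. Under the stated assumptions, about 2 to 5 of 20 treated participants would be counted in the upper group while at or below 35 when the month-6 cytokines are drawn. The conflict between 30 and 35 is plain from the text and needs no assumption. Its effect under the any-reading rule is small, about 0.2 to 1.2 of 20. The existence of both defects is certain; their size depends on a distribution of 25-OH levels that the documents do not give. The point applies to any achieved-level immune analysis, whether primary or supportive.

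**What to change.** 1. In any achieved-level immune analysis, use the month-6 25-OH value, scheduled at the same visit as the cytokines, and enter it as a continuous variable. This removes both the timing ambiguity and the cut-off. The small downside is that it assumes an approximately linear relation, which should be checked.
2. If a two-group split is kept, base it on the month-6 value and state one analysis definition of sufficiency.
3. Reconcile 30 and 35 across the Specific Aims, the section B discussion of dosing, Research Design and Methods, Basic Information items 1 and 2, and the Immune Function Analysis. Which value is right, and whether the dosing text changes, is for the sponsor; nothing here prescribes a dosing rule.
4. Keep this separate from the comparison by randomized arm in SA4, which it does not replace.

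The cost is a change of wording. No extra samples or visits are needed, since Table 1 already includes vitamin D at month 6.

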SA1: To compare functional performance benefit between HD participants randomized to vitamin D supplementation and placebo. Function will be measured by the 50ft timed walk, the Timed Up and Go test (TUG), a timed stair climb, the Chair Raise test, the Functional Reach test, postural sway, and muscle handgrip, hip flexor and knee extensor strength.

H1: We hypothesize that a greater proportion of the subjects will demonstrate an improvement in postural sway in the treatment group than in the placebo group.

SA2: To compare cognitive function as measured by neuropsychological testing between HD participants randomized to vitamin D supplementation and placebo.

H2: We hypothesize that a greater proportion of the subjects will demonstrate an improvement in the treatment group than in the placebo group.

SA3: To compare the Self-report of physical activity and quality of life (QOL) between HD participants randomized to vitamin D supplementation and placebo.

H3: We hypothesize that the total score on the Physical Activity Scale for Persons with Physical Disabilities (PASIPD) and the QOL scores will significantly improve in the treatment groups versus no change in the control group.

SA4: To compare immune function between HD participants randomized to vitamin D supplementation and placebo.

H4: We hypothesize that immune function will be increased in the treatment group versus no change in the control group.

B) BRIEF REVIEW OF RESULTS OF OTHERS AND CURRENT STATE OF KNOWLEDGE

Pathophysiology and Management of Vitamin D and Deficiency in HD Patients:

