Blood draws for vitamin D and B12 Folate levels will require about 5 ml of blood for each draw. All Vitamin D levels will be determined by Quest Laboratories. B12 Folate levels will be determined by kit assay in [name] core laboratory as part of the CMCSCI. Vitamin D levels will be tested twice to establish baseline values. Vitamin D levels will be tested once a month during the treatment phase for safety monitoring. B12 Folate levels will be tested at baseline and 6 months. Blood draws for immune function tests will take place during dialysis sessions at baseline and 6 months. These tests will require a total of a 43cc draw. Immune function measurements include serum cytokines.

Chart review A chart review will be performed for all participants. The chart reviews will be performed by [name] (PI). No subject time commitment is required for the chart reviews.

3. Describe population to be studied, listing basis for selection or exclusion. Include number to be studied.

Individuals with advanced chronic kidney disease on hemodialysis (HD) will be studied. Thirty participants will be studied: 20 in the treatment group and 10 in the placebo group. Enrolled patients will be randomized into either the treatment or placebo group.

4. If subjects are patients, will conventional therapy or diagnostic procedures be withheld or modified for the purpose of this study?

If participants in this study are patients, conventional therapy or diagnostic procedures will not be withheld or modified. All participants will receive their normal care throughout their involvement in research.

b. List Possible RISKS

1. List possible hazards to subjects and/or investigative personnel from the procedures, drugs, or isotopes to be employed.

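### The immune analysis does not say how the baseline cytokine is used, and it compares attained vitamin D groups although H4 is about the randomised arms

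*Combined protocol and SAP*

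**What the plan says.** H4 in section A (Specific Aims) is a statement about the randomised arms and about change: "We hypothesize that immune function will be increased in the treatment group versus no change in the control group". The arms are set in section C, Research Design and Methods: "Enrolled participants will be randomized 2:1 to receive vitamin D (n=20) or placebo (n=10) for 6 months".

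The outcome is described only in general terms: "Immune function measurements include serum cytokines". No cytokine, scale or direction is named. On timing, section C.a.2 says "Blood draws for immune function tests will take place during dialysis sessions at baseline and 6 months", and Table 1 agrees.

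The Immune Function Analysis paragraph then sets a different comparison: "Primary analysis will compare study subjects who had a 25-OH level > 35 ng/ml to study subjects who remained at a level" of 35 ng/ml or below. It lists the candidates for adjustment: "Potential confounders that will be examined include age, 25-OH Vitamin D level at Baseline, time on HD, sex, and ethnicity". Its entry rule admits "Variables that differ significantly between treatment arms at an alpha of 0.01 and are significantly related to the immune outcomes at an alpha of 0.05". If any candidate qualifies, the multivariable model becomes the primary analysis.

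The percent-change rule in the Statistical Analysis Plan is given for the functional primary outcomes and the self-assessment scales. It is not extended to cytokines.

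The only infection criterion is the fourth exclusion at entry, "receiving intravenous antibiotics for infection". Nothing is said about infection at the month-6 draw.

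**The concern.** A patient's own baseline cytokine is usually among the best predictors of the later value, and this trial collects it. An analysis that does not say how it is used leaves the analyst to choose between a month-6 comparison, a change score, a percent change and an adjusted model after the data are seen. With 30 patients these can give different answers.

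The grouping matters more. Attained 25-OH level is a post-randomisation variable. Entry requires a level below 25 ng/ml, so the lower group would hold most or all placebo patients plus every treated patient who did not exceed 35. Patients who respond to a fixed regimen may differ from those who do not in nutrition, inflammation or adherence to dialysis, and each of these could be related to cytokines. The comparison is then not protected by randomisation and does not test H4 as written.

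The confounder screen does not repair this. It looks for imbalance between the treatment arms, whereas the groups compared are defined by attained level.

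**Working it through.** **Plan's own figure.** There is none for H4. The sample sizes in the Power analysis (26, 22 and 18) belong to the functional responder endpoint. No SD, correlation, effect size or infection rate is given for cytokines, so the inputs below marked *assumed* are mine.

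**1. Would the screen admit baseline cytokine if it were listed?** Under randomisation, a baseline variable differs between arms at alpha 0.01 about 1% of the time. It must also pass the outcome test at 0.05, so the chance of entry is at most about 1%, however strongly it predicts the outcome.

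**2. Who is in the two groups?** For illustration, the protocol's dosing review cites hemodialysis studies in which 57% to 94% of patients exceeded 30 ng/ml (other regimens, and a lower cut-off than 35). If those fractions applied to the 20 treated patients, 20 × 0.06 = 1.2 to 20 × 0.43 = 8.6 of them would join the 10 placebo patients. The lower group would then number about 11 to 19, with about 1 to 9 of them on vitamin D.

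**3. Gain from baseline adjustment.** Take rho, the baseline-to-month-6 correlation on the log scale, as 0.5 to 0.7 (*assumed*), with equal SD at both times.

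| Variance (units of SD²) | Formula | rho 0.5 | rho 0.7 |
|---|---|---|---|
| Month-6 value only | 1 | 1.00 | 1.00 |
| Change score | 2(1 − rho) | 1.00 | 0.60 |
| Baseline-adjusted | 1 − rho² | 0.75 | 0.51 |
| Adjusted ÷ month-6 only | 1 − rho² | 0.75 | 0.51 |
| Adjusted ÷ change score | (1 + rho)/2 | 0.75 | 0.85 |

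Against a month-6-only analysis, this is like having 1/0.75 = 1.3 to 1/0.51 = 2.0 times the patients. Against a change score it is 1/0.85 = 1.2 to 1/0.75 = 1.3 times.

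At 20 against 10, the difference detectable with 80% power (two-sided 0.05, normal approximation) is (1.96 + 0.84) × √(1/20 + 1/10) = 2.80 × 0.387 = 1.09 SD unadjusted. Multiplying by √0.75 and √0.51 gives about 0.94 and 0.77 SD adjusted.

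**4. Infection at the month-6 draw.** *Assumed*: a fraction f = 0.05 to 0.10 of draws infected, an m = 3 to 5 fold rise, and log SD 0.8 (variance 0.64). Added variance is f(1 − f)(ln m)².
- Low: 0.0475 × 1.207 = 0.057. High: 0.09 × 2.590 = 0.233.
- Unadjusted: √(1 + 0.057/0.64) = 1.04 to √(1 + 0.233/0.64) = 1.17, so the standard error rises 4% to 17%.
- Adjusted: √(1 + 0.057/0.48) = 1.06 to √(1 + 0.233/0.326) = 1.31, so it rises 6% to 31%.

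One infected patient among 10 placebo patients shifts that arm's log mean by ln 3/10 = 0.11 to ln 5/10 = 0.16. The unadjusted standard error is 0.8 × 0.387 = 0.31, so the shift is 0.35 to 0.52 standard errors.

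The chance of two or more infected in placebo and none among the 20 treated is 0.086 × 0.358 = 0.031 at f = 0.05 and 0.264 × 0.122 = 0.032 at f = 0.10, about 3% in both cases.

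**5. Simulation (5,000 runs, 20 against 10, rho 0.7, no true effect).** Infected values were raised by 2 to 3 SD. This is severe: a 5-fold rise is ln 5/0.8 = 2.0 SD.

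| Infected, all in the group of 10 | False positives, month-6 only | False positives, adjusted |
|---|---|---|
| 1 | 6–7% | 6–8% |
| 2 | 12–18% | 15–24% |
| 3 | 24–39% | 34–54% |

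With infection equally likely (10%) in both groups, type I error stays near 5%. Power for a 1-SD effect falls from 70% to 46–58% (month-6 only) or from 93% to 57–75% (adjusted). Baseline adjustment therefore does not cure month-6 infection, which needs its own handling.

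**The case against.** **Baseline may be meant to enter through change.** H4 speaks of an increase against no change, and cytokines are drawn twice. The Statistical Analysis Plan also mentions a baseline-versus-6-month repeated-measures ANOVA for secondary analyses, although its age- and education-adjusted T scores point to the cognitive tests. A reader might infer that the plan discards the baseline cytokine. The documents do not support that; they leave its use unspecified. If change was intended, the gain from adjustment is the smaller one, 0.75 to 0.85 of the variance.

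**Infection could be thought decisive.** A reader might infer that infection is screened out at entry and then admitted at month 6, so that a few infected patients decide H4, each carrying a tenth of the placebo mean. This goes too far on three counts. Entry excludes only patients on intravenous antibiotics, so baseline is not free of infection. The planned comparison is by attained level, so a tenth of the placebo mean is not a quantity the plan uses. One case moves the result little, and the one-sided clustering needed for a false positive is uncommon at the assumed rates.

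**Removing infected draws has its own risk.** Infection arises after randomisation and might itself be affected by treatment, so exclusion can bias. Postponement is limited too: supplementation lasts 6 months, and a later draw could fall after dosing ends. Both points stand and shape the fix.

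**This is a secondary outcome in a 30-patient pilot.** That is true and limits the weight of the point. It does not justify leaving the comparison undefined when one sentence settles it.

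**Conclusion.** The concern holds in a limited form. Two facts rest on the text alone: the use of baseline cytokine is unspecified, behind a screen that would almost never admit it, and the primary immune comparison is not the one H4 describes. The second is the more serious, because no covariate choice turns an attained-level comparison into a randomised test.

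The size of the precision gain depends on an assumed correlation of 0.5 to 0.7. The infection gap is real but secondary: under the assumed rates and rises it inflates the standard error by 4–17% unadjusted or 6–31% adjusted. With equal risk in both arms it costs power and leaves type I error near 5%. The change should be made, in proportion to a secondary outcome of a pilot.

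**What to change.** 1. Make the primary immune analysis a comparison of log month-6 cytokine between the randomised arms, with log baseline cytokine as a fixed covariate exempt from significance screening. Name the cytokine or cytokines, and the direction that counts as increased immune function, in advance.
2. Keep the comparison above and at or below 35 ng/ml as exploratory, labelled as non-randomised.
3. At the month-6 research draw, record whether the patient is on intravenous antibiotics or otherwise infected. Keep all draws in the primary analysis and repeat it without flagged draws as a sensitivity analysis only. If a research draw is postponed, keep it within the supplementation period.

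The cost is a few lines in the analysis plan, one recorded item at month 6 and one residual degree of freedom (28 to 27 with all 30 patients). No treatment changes and no extra blood is taken.

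### The immune analysis compares patients by achieved 25-OH level but screens confounders between treatment arms at alpha 0.01, so this non-randomised comparison will almost always be reported unadjusted

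*Combined protocol and SAP*

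**What the plan says.** SA4 in the Specific Aims is a comparison by randomised arm: "To compare immune function between HD participants randomized to vitamin D supplementation and placebo". The Immune Function Analysis paragraph at the end of the Statistical Analysis Plan uses a different grouping: "Primary analysis will compare study subjects who had a 25-OH level > 35 ng/ml" with those at or below 35. It does not state the visit at which the level is judged.

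Five candidates are named: "Potential confounders that will be examined include age, 25-OH Vitamin D level at Baseline, time on HD, sex, and ethnicity". A candidate enters the model only if it meets two conditions together. It must belong to the "Variables that differ significantly between treatment arms at an alpha of 0.01", and it must be among those that "are significantly related to the immune outcomes at an alpha of 0.05". The paragraph then adds: "If potential confounders meet the criteria for inclusion, the multivariable analysis will be the primary analysis". If nothing qualifies, the unadjusted comparison stays primary.

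No covariate is fixed in advance. Serum cytokines are measured at baseline and 6 months (Secondary Outcomes; Table 1), but the baseline value is not among the candidates. The paragraph does not say whether the outcome is the 6-month value or a change from baseline.

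**The concern.** Achieved level is not randomised. The group at or below 35 will mix placebo patients with treated patients who did not reach the target. Whatever helps a treated patient pass 35, baseline 25-OH being the obvious example, will differ systematically between the two level groups. If it also relates to cytokines, it confounds the comparison.

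A check between randomised arms cannot detect this, because randomisation balances the arms on average however strongly a variable drives achieved level. The plan would then report a confounded comparison, unadjusted, as its primary immune result. A reader could take a difference produced by patient characteristics as an effect of vitamin D on immune function, and the pilot is meant to inform a pivotal trial.

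**Working it through.** The plan gives no power or precision figure for the immune analysis. Its only sample-size figures (26, 22 and 18) concern the functional responder outcome and do not enter here.

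**Inputs from the documents.** Allocation is 20 vs 10 (Research Design and Methods). The permitted dropout of 33% (Power analysis) leaves about 20 patients, or roughly 13 vs 7. There are five candidates, with screening alphas of 0.01 and 0.05, taken as two-sided. In the cited dosing studies used here, 57% and 87% of patients passed 30 ng/ml; these serve as a proxy for passing 35.

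**How often the arm test passes.** As randomised, the arms differ only by chance.
- One variable: 0.01.
- Any of five, if independent: 1 − 0.99^5 = 0.049.
- Any of four, if sex is constant (the unit's earlier sample was all male): 1 − 0.99^4 = 0.039.
- One variable unrelated to the outcome, both conditions: 0.01 × 0.05 = 0.0005.

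**Observed gap needed for p < 0.01.** For a continuous covariate the gap in SD units is t(0.995, n1+n2−2) × √(1/n1 + 1/n2).
- 20 vs 10: 2.763 × √0.15 = 1.07 SD.
- 13 vs 7: 2.878 × √0.2198 = 1.35 SD.

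**Effect on the comparison actually made.** Simulation with N = 30 (20:10), no effect of treatment or of level on the cytokine, and 100,000 runs per scenario. One baseline covariate has correlation 0.3, 0.5 or 0.7 with the outcome, and 0.5 or 0.7 with the latent variable that decides whether a treated patient passes 35. Of the treated, 57%, 75% or 87% pass; no placebo patient does. The correlations, the 75% and the zero placebo rate are assumptions. Four of the 18 scenarios:

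| Corr. with outcome | Corr. with passing 35 | Treated passing | Gap between level groups (SD) | Screen admits covariate | Type I: no adjustment | Type I: plan's screen | Type I: screen on level groups | Type I: fixed adjustment | Type I: by arm, unadjusted |
|---|---|---|---|---|---|---|---|---|---|
| 0.3 | 0.5 | 87% | 0.28 | 0.4% | 0.056 | 0.055 | 0.054 | 0.050 | 0.050 |
| 0.5 | 0.5 | 75% | 0.42 | 0.9% | 0.084 | 0.083 | 0.070 | 0.050 | 0.050 |
| 0.5 | 0.7 | 57% | 0.77 | 0.8% | 0.165 | 0.163 | 0.093 | 0.049 | 0.049 |
| 0.7 | 0.7 | 57% | 0.77 | 1.0% | 0.291 | 0.288 | 0.133 | 0.049 | 0.049 |

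Across all 18 scenarios:
- The level groups differ by 0.28 to 0.77 SD on the confounder, and the arm-based screen admits it 0.4% to 1.1% of the time.
- Type I error is 0.055 to 0.288 with the plan's screen and 0.056 to 0.291 with no adjustment.
- Applying the same screen to the level groups gives 0.054 to 0.133.
- Fixed adjustment gives 0.048 to 0.051.
- Comparison by randomised arm gives 0.049 to 0.052, adjusted or not.

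**Precision from the baseline cytokine.** Let ρ be the baseline-to-6-month correlation, with equal variances.
- Against an unadjusted 6-month value, ANCOVA removes ρ² of the variance: 25% at ρ = 0.5 and 49% at ρ = 0.7.
- Against a simple change score, the variance ratio is (1 − ρ²) / [2(1 − ρ)] = (1 + ρ)/2, so the reduction is (1 − ρ)/2: 25% at 0.5 and 15% at 0.7.

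Both values of ρ are assumed.

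**The case against.** **Treatment arms may be loose wording.** The sentence follows directly on the achieved-level comparison, so the phrase could mean the two level groups. Elsewhere the plan uses arms for the randomised assignment, so the literal reading is the stronger one, but the wording should be settled. On the loose reading the upper type I error falls from 0.288 to 0.133. That is better, but still not controlled.

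**The inflation comes from the grouping, not from the screen.** Largely true: comparing by arm holds 0.05 with or without adjustment. But the screen is the plan's only safeguard for the grouping it chose, and it gives almost no protection.

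**The model switch is written in advance and rarely operates.** This stands. A reader might infer that the analyst may choose the primary model after seeing results. The text gives no such discretion: the candidates, both alphas and the consequence are fixed. The near-identical error rates with the screen and with no adjustment show that the switch itself does little harm.

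**Low power of the screen.** A reader might compute that a 0.01 test at 20 vs 10 detects a true 0.5, 0.8 or 1 SD imbalance only 9%, 26% or 44% of the time, and infer that real imbalances between arms go unadjusted. Randomisation rules out a true imbalance between the arms as allocated, so these figures do not measure the problem. The 1% pass rate does.

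**Weight.** Cytokines are the last-listed secondary outcome of a 30-patient feasibility study. That limits the priority of the point but does not remove it: H4 is a stated hypothesis, and the correction uses data already collected.

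**Conclusion.** The point holds in this form. The primary immune comparison is non-randomised and departs from SA4, and its covariate screen, read literally, examines a different grouping. The comparison would almost always be reported unadjusted, even when a listed variable confounds it.

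The pass rates (1% per variable, at most 4.9% for any of five) follow from randomisation and the stated alpha; the 4.9% assumes independent candidates. The type I error range of about 0.055 to 0.29 depends on the assumed correlations, the assumed attainment among treated patients and zero placebo attainment. At the mild end the inflation is negligible.

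Two further inferences go beyond the documents. The plan does not ignore confounding: it names five candidates, including baseline 25-OH, but handles them poorly. Nor can a 25% to 49% precision gain from the baseline cytokine be claimed outright, because the form of the outcome is not stated and the gain over a change score is smaller at the higher correlation.

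**What to change.** Drop the significance screen and the rule that changes which model is primary. Make the primary immune analysis an ANCOVA of the 6-month cytokine value by randomised arm, with the baseline cytokine value as a fixed covariate. Baseline 25-OH may be added as a second fixed covariate but is optional. The analysis scale should be stated in advance; the documents give no cytokine distribution from which to require a particular one.

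Keep the comparison above and below 35 ng/ml as exploratory, with baseline cytokine and baseline 25-OH fixed as covariates and the visit that defines the level stated. Note that unmeasured confounding remains, since fixed adjustment deals only with what is measured.

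The cost is SAP wording, one or two degrees of freedom, and the loss of primary status for the achieved-level comparison. No new data are needed.
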